6.7 Injection (Step 2) Safety Population

All Safety Population participants who receive at least one injection

6.8 Longitudinal Pharmacokinetic CAB Concentration Population

A longitudinal evaluation of CAB PK in the CAB arm will be conducted in 150 participants, excluding any participant who has had any positive HIV testing at any visit (exclude HIV final status= "positive" or "additional testing needed"). Participant selection should be limited to participants who have reached week 57 before 3.1.2020 and have no late injections beyond 2 weeks of target date prior to week 57. The window for late injections is defined as 2 weeks after target date. Selected participants should have no missed injections (including regular injection visits, as well as no missing injection). These 150 participants present the following distribution across sites:

- 40% cisgender women <25 years of age at enrollment
- 40% cisgender women between 25 and 30 years of age at enrollment
- 20% cisgender women ≥ 30 years of age at enrollment

This population will be used for the CAB concentration listing and to enhance the population represented in the global modelling of CAB-LA PK.

6.9 TDF-FTC Adherence Population

The TDF-FTC adherence population consists of approximately 400 participants in the TDF/FTC arm who were randomly selected for assessment of adherence to oral pill taking. To achieve balance across geographic regions and balance over time, selection of the Adherence Population was stratified by study sites or regions and was selected throughout the enrollment period by randomly choosing approximately 25% of all new enrollees in the TDF/FTC arm each quarter. Plasma and DBS samples for selected follow-up visits are tested for TFV and FTC throughout the follow-up period.

6.10 Contraceptive Substudy Population

All participants who are invited and agree to participate in the Contraception sub study.

6.11 Pregnancy Population

All participants who have a positive pregnancy test result while on treatment.

6.12 Confirmed Pregnancy Population

All participants who have a positive pregnancy test result while on treatment that is followed by a positive confirmatory test result or confirmation by another method. (Ultrasound, full- or pre-term live birth.).

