2.7.4. Pregnancy

A participant with a first positive pregnancy test will temporarily discontinue blinded injections and receive a 4-week supply of open label TDF/FTC and may resume blinded treatment if a second test after 4 weeks indicates that she is not pregnant. All pregnant participants with a confirmed positive pregnancy test (four weeks after the initial pregnancy test) will be unblinded and followed by the study every 12 weeks. Regardless of the randomization assignment or point in the study, all pregnant participants will be placed on open-label TDF/FTC for the duration of the pregnancy. Once pregnancy outcome is reached, and after the participant is not breastfeeding, she may resume study product, according to original randomized arm but open-label, and resume visits per the study schedule.

If participants decline to use an approved contraceptive method, they will be given open-label TDF/FTC for 48 weeks starting no later than eight weeks after her last CAB LA/placebo injection. If study follow-up is ongoing she will be required to be followed up at least annually for HIV testing thereafter. If a participant transitioned to open-label TDF/FTC during Step 2, either because she wanted to become pregnant or declined to continue using long-acting contraception, and subsequently changes her mind she may continue in the study on blinded study product (per original randomization) once she has documentation of a negative pregnancy test and of resuming long-acting contraception.

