Data from steps 1 and 2 (PRIMARY mITT dataset) will be used. Tables will summarize the number of pregnancies and pregnancy rate by arm. The pregnancy rate and 95% robust confidence interval for each treatment arm will be calculated using a log-linear model for counts using log(person-time) (excluding time spent pregnant) as an offset, assuming a Poisson distribution, and using a robust variance (i.e. generalized estimating equations).

Outcomes of all detected pregnancies (PREGNANCY dataset) and all confirmed pregnancies (CONFIRMED PREGNANCY dataset), including information of drug exposure during the conception period and pregnancy period, will be tabulated by arm.

e. **Objective:** To evaluate rates of HIV drug resistance among participants who acquire HIV infection during the study among participants receiving oral CAB/CAB LA vs. oral TDF/FTC.

Population: Primary SEROCONVERTER Population

Data from steps 1, 2 and 3 will be included. The number of cases of drug resistance will be summarized by arm and step. All cases of drug resistance among incident HIV infections during the study will be described.

f. **Objective:** To determine plasma concentrations of medroxyprogesterone (DMPA) or norethisterone (NET-EN) or etonorgestrel (from implants) when co-administered with CAB LA.

Population: CONTRACEPTION Subgroup Population

Outcome: Plasma concentration of medroxyprogesterone or norethisterone.

Boxplots of plasma concentrations of DMPA/NET_EN/etonorgestrel will be generated by arm. For women in the CAB-LA arm, a plot of plasma concentrations versus time since last injection will be plotted and a smooth line will be fit through the data. Proportion of women with plasma concentrations below 0.1 ng/mL (DMPA) or TBD (NET_EN) or 90pg/mL (etonorgestrel) will be reported and compared (separately, for women using each drug) between arms using a Fisher's exact test or a permutation test if multiple observations are available on each woman.

In addition, we will compare mean contraceptive drug levels (and/or other PK parameters) between the CAB LA and TDF/FTC arms for each contraceptive subgroup using a t-test (or a t-test with robust variance if multiple observations on each woman are available).

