- Day 0 for Open Label Truvada Schedule may be a Step 2 visit code or 201. See Section 13.5 Alternate Visits.

Pregnancy Schedule*						
Week	Visit Code	Day allowable window opens	Day target window opens	Target Day	Day target window closes	Day allowable window closes
Day 0 (First positive Pregnancy Test)	XX.X	0	0	0	0	0
4 weeks after first positive pregnancy test	Interim visit XX.X	21	--	28	--	35

Quarterly Visit 1 (12 weeks since first positive pregnancy test)	101	43	70	84	98	126
Quarterly Visit 2 (24 weeks since first positive pregnancy test)	102	127	154	168	182	210
Quarterly Visit 3 (36 weeks since first positive pregnancy test)	103	211	238	252	266	294

*Pregnancy schedule is to be followed throughout pregnancy and while participant is breastfeeding.

Yearly/Annual Visits						
Week	Visit Code	Day allowable window opens	Day target window opens	Target Day	Day target window closes	Day allowable window closes
Day 0 (Last visit participant at clinic HIV Test conducted)	XX.X	0	0	0	0	0
Yearly Visit 1	50.0	182	358	365	372	548
Yearly Visit 2	51.0	547	723	730	737	913
Yearly Visit 3	52.0	912	1088	1095	1102	1278
Yearly Visit 4	53.0	1277	1453	1460	1467	1643
Yearly Visit 5	54.0	1642	1818	1825	1832	2008

Seroconverter Schedule						
Week	Visit Code*	Day allowable window opens	Day target window opens	Target Day	Day target window closes	Day allowable window closes
HIV Confirmatory Visit	XX.X	0	0	0	14	42
Week 12	XX.X	43	70	84	98	126
Week 24	XX.X	127	154	168	182	210
Week 36	XX.X	211	238	252	266	294
Week 48	XX.X	295	322	336	350	378

*Due to unblinding considerations, there are no unique visit codes for seroconverters. The visit codes should reflect the next study visits for the participants.

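### Section 6.12 lets a live birth, but no pregnancy loss, confirm a pregnancy, so the confirmed-pregnancy outcome table, read alone, can understate loss

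*SAP*

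**What the plan says.** The SAP defines two pregnancy sets.

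- **Section 6.11, Pregnancy Population:** "All participants who have a positive pregnancy test result while on treatment". No confirmation is needed.
- **Section 6.12, Confirmed Pregnancy Population:** the positive test must be one that "is followed by a positive confirmatory test result or confirmation by another method. (Ultrasound, full- or pre-term live birth". No form of pregnancy loss is named. Section 10.2.7 says this text was added in Version 4.0 to give further ways of confirming a pregnancy.

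Section 6.12 puts no time on the confirmatory test. Section 2.7.4 does, describing a "confirmed positive pregnancy test (four weeks after the initial pregnancy test". In Appendix A the pregnancy-schedule row "4 weeks after first positive pregnancy test" has target day 28 and an allowable window of days 21 to 35. Under section 2.7.4 a woman with a first positive test "may resume blinded treatment if a second test after 4 weeks indicates that she is not pregnant".

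Section 7.3.7(d) uses both sets: "Outcomes of all detected pregnancies (PREGNANCY dataset) and all confirmed pregnancies (CONFIRMED PREGNANCY dataset" are to be tabulated by arm, with drug exposure around conception and during pregnancy.

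**The concern.** A set used to describe pregnancy outcomes should not select on those outcomes. Under 6.12 a live birth can confirm a pregnancy after the fact, but a loss cannot. A pregnancy that ends in the roughly four weeks between the first and second test may leave neither a second positive test nor an ultrasound. Even with the loss on record, the listed methods do not let it in.

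Comparing pregnancy outcomes between arms is a stated tertiary objective (section 3.3), and 7.3.7(d) asks for outcomes alongside exposure around conception. Losses soon after detection lie closest to that exposure, and they are the ones most easily left out of the confirmed table. A reader who takes that table as the clean one would see too low a share of losses.

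**Working it through.** The SAP states no figure for pregnancies, losses, ultrasound use or false-positive tests, so there is nothing to reproduce. The check has two parts: the logic of the definition, and arithmetic on assumed rates.

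**1. Same test history, different outcome.** Take a woman with one positive test on treatment, no second positive test and no ultrasound.

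| Documented outcome | In 6.11? | In 6.12? |
|---|---|---|
| Live birth, term or pre-term | yes | yes |
| Spontaneous or induced abortion | yes | no |
| Ectopic pregnancy | yes | no |
| Stillbirth | yes | no |

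A loss with a second test still positive, or with an ultrasound, is confirmed and stays in. The gap is limited to losses with neither.

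**2. Direction of the error.** Per 100 true detected pregnancies, let e be lost without confirmation and l be lost after confirmation.

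- True loss share = (l + e)/100
- Loss share in the confirmed set = l/(100 − e)

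The confirmed share is never above the true one: (l + e)(100 − e) − 100·l = e(100 − l − e), which is zero or positive. It is zero when e = 0.

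**3. Size under assumed values.**

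| l | e | Confirmed set | True |
|---|---|---|---|
| 10 | 0 | 10/100 = 10.0% | 10% |
| 10 | 5 | 10/95 = 10.5% | 15% |
| 10 | 10 | 10/90 = 11.1% | 20% |
| 10 | 20 | 10/80 = 12.5% | 30% |
| 15 | 5 | 15/95 = 15.8% | 20% |
| 15 | 10 | 15/90 = 16.7% | 25% |
| 15 | 20 | 15/80 = 18.8% | 35% |

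**4. Difference between arms.** Assume unconfirmed early loss of 10% in one arm and 5% in the other, with 10% of the remainder lost later in both. True totals are 0.10 + 0.90 × 0.10 = 19.0% and 0.05 + 0.95 × 0.10 = 14.5%. The confirmed set shows 10% in each arm.

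**5. The all-detected table.** Add 10 false-positive first tests to 100 true pregnancies with l = 10 and e = 10. The loss share is 20/110 = 18.2% if the false positives are not counted as losses and 30/110 = 27.3% if they are, against a true 20%. The SAP gives no rule for coding them. For the two arms in step 4, with 10 false positives per 100 in each and none coded as a loss, the table shows 19/110 = 17.3% and 14.5/110 = 13.2%. The difference is diluted but still visible.

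**6. What a broader list would recover.** If a fraction d of the e losses is documented and accepted as confirming, the confirmed share becomes (l + d·e)/(100 − (1 − d)·e). For l = 10 and e = 10, d = 0.5 gives 15/95 = 15.8%, and d = 1 gives 20/100 = 20%, the true value.

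**The case against.** The strongest reply is that the two tables are meant as a pair. The all-detected set is sensitive and the confirmed set is specific, and it is unfair to fault the second for being specific. Women with an early loss are not dropped from the analysis; they stay in 6.11, and their outcomes are tabulated by arm. Step 5 shows that a difference between arms could still be seen there. This stands, and it is why the point is minor. It does not remove the asymmetry: excluding false-positive tests does not require excluding documented losses, and the all-detected share depends on a coding choice that the SAP leaves open.

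The parenthesis in 6.12 might also be read as examples, so that a documented loss would count as another method. That is possible. But section 10.2 says Version 4.0 was prepared for Clinical Study Report programming, and a programmer would probably code the items as a closed list. On either reading the wording needs settling.

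Stillbirth is a late outcome and would ordinarily follow a positive four-week test, so its absence matters mainly when that visit was missed. This stands too.

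Two stronger readings are tempting and not supported.

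- A reader might infer from 2.7.4 that early losses are analysed as not pregnant. That sentence governs resumption of blinded product; it does not classify women for analysis.
- A reader might connect the definition to Safety in Pregnancy, an adverse event of special interest in Appendix E. That item is identified from adverse event terms reported with pregnancy exposures to CAB, not from the 6.12 set.

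**Conclusion.** The point holds in a limited form. Section 6.12 selects partly on the outcome that 7.3.7(d) tabulates, and the error can only run towards understating loss in the confirmed-pregnancy table when that table is read alone.

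Its size is unknown. Every percentage above rests on assumed rates, none of them from the SAP, and the understatement is zero if every loss has a second positive test or an ultrasound. Nothing in the document shows that unconfirmed early loss will be common or will differ between arms.

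The effect is confined to one descriptive table under a tertiary objective. It does not touch the primary analyses, the adverse events of special interest or the clinical handling of a positive test. Whether it reaches the pregnancy rate cannot be said: the line "Tables will summarize the number of pregnancies and pregnancy rate by arm" does not state whether detected or confirmed pregnancies are counted.

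**What to change.** 1. In 6.12, accept any documented pregnancy outcome as confirmation: live birth, stillbirth, spontaneous or induced abortion, or ectopic pregnancy, alongside a second positive test or an ultrasound. State that the list is complete.
2. In 7.3.7(d), show by arm the first positives that had no second positive test, ultrasound or live birth, split into documented loss (now counted as confirmed), no evidence of pregnancy, and unknown. This also lets the all-detected table be read without guessing how false positives were coded.

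The cost is SAP wording, one population flag and one added table, provided that pregnancy outcomes are recorded for women without a confirmatory test; the case report forms are not available to check this. The downside is that a few early pregnancies documented only by a recorded loss may enter the set, and the reported loss share may rise slightly. Undocumented losses would still be missed, as step 6 shows. No change to clinical management is involved.

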6.13 Declined contraception population

All participants who decline to use long-acting contraception at any point during step 1 or 2 after LOA 3 to protocol v1.0 was implemented.

6.14 Seroconverter Population

All ITT participants who, during the course of the trial, are either identified to have been HIV infected prior to randomization, or who acquired HIV infection during trial the primary analysis follow-up period.

6.15 Primary Seroconverter Population

All ITT participants who are HIV-uninfected at randomization and acquire HIV infection during the primary analysis follow-up period.

6.16 Infected at Enrollment Population

All ITT participants who were subsequently determined to be HIV-infected at randomization.

6.17 Subgroups

Important participant subgroups are

- Age:<25 vs \geq 25 years old
- HSV-2 status at baseline*
- Method of contraception during follow-up**
- BMI $</\geq$ 30 kg/m²

* Note: HSV-2 status at baseline will not be available for the Clinical Study Report

**Note: Contraceptive method will be modeled as a time-dependent covariate. This analysis will not be presented in the Clinical Study Report.

7. STATISTICAL ANALYSES

7.1 General Analysis Considerations

Any deviations from the original statistical plan will be described in the final report.

7.1.1. *Summary Statistics*

Summary statistics for categorical variables will include frequency and percentage. For continuous variables, number of subjects with non-missing value (n), mean, median, standard deviation (SD), minimum (min), and maximum (max) will be reported. For change from baseline calculations, baseline is defined as Day 0/Randomization visit. If a baseline value is not available from the randomization visit, for certain parameters the baseline value may be obtained from the enrollment visit.

7.1.2. *Visit Windows*

All data will be tabulated per the evaluation visit as recorded on the CRF even if the assessment is outside of the visit window. Visit windows are displayed in Appendix A. In

data listings, the relative day, of all dates will be presented e.g. from date of randomization, or date of last injection.

7.2. Interim Analyses

An independent Data Safety and Monitoring Board (DSMB) will meet approximately every six months throughout the study. The DSMB will do the following:

- I. Periodically review and evaluate the accumulated study data for participant safety, study conduct and progress and treatment efficacy.
- II. Make recommendations to the study investigators and DAIDS concerning the continuation, modification, or termination of the trial.

The DSMB will consider study-specific data as well as relevant background knowledge about the disease, test agents and patient population under study.

Analyses presented to the DSMB will include information on accrual and retention, comparability of the CAB LA and TDF/FTC arms at enrollment, and adherence, adverse events and HIV incidence by arm. The DSMB may also ask for additional analyses they deem relevant.

Below we provide guidelines for monitoring HPTN 084 for:

Study progress and validity	Futility monitoring
Efficacy monitoring	Safety monitoring

7.2.1. *Study progress and validity*

At each meeting the DSMB will review data on enrollment (as necessary), retention of participants, delivery of the intervention and all protocol violations. The DSMB will also compare the (pooled) observed HIV incidence rate to the (pooled) expected HIV incidence rate to determine if the HIV incidence rate among study participants is similar to the incidence rate assumed in the study design. The DSMB will recommend any changes to the study design they believe are needed to ensure study validity.

Expected event rate: 2.07/100 person-years in the TDF/FTC arm and 1.12/100 person-years in the treatment arm; 1.6/100 person-years overall. Note: In general, person-years are calculated as the sum of the total follow-up time for all participants included in the analysis, using the censoring rules as described for each individual analysis. Start and end dates and censoring rules for the primary analysis are defined in Appendix B.

7.2.2. *Efficacy monitoring*

This analysis determines the Sample Size of the study, therefore kindly refer to section 4.1.1 of the SAP.

7.2.3. *Futility monitoring*

The DSMB may determine that the trial is operationally futile if enrollment rates are substantially lower than expected (such that accrual cannot be completed in a timely manner) or retention is so poor that results of the trial would lack validity.

However, other aspects of the trial which are typically evaluated for futility (low HIV event rate, lack of difference between the arms) must be evaluated in the context of participant adherence to the study drugs. While high adherence is expected in the CAB LA arm, high rates of adherence in the TDF/FTC arm would likely lead to a lower than expected HIV event rates and little difference in HIV incidence between the arms. Such a result should

not lead to a futility finding. While HPTN 084 is designed as a superiority trial, a contingency plan for a supplementary non-inferiority analysis in the case of high TDF/FTC adherence has been developed. This analysis is described in detail in the **protocol HPTN 084 v2.0, in the section 7.8.4 entitled “Considerations for a Supportive Analysis if Adherence to TDF/FTC is Higher than Expected”**. To aid in this evaluation, detailed information on adherence to the study drugs, by arm, will be provided to the DSMB.

7.2.4. Safety monitoring

At each 6 months visit the DSMB will be provided with a list of all adverse events, by grade and broken down by study arm. The relationship of the event to the treatment (definitely related, probably related, possibly related, not related) will also be described. In the closed report at each visit the study team will provide the DSMB with a (nominal) p-value comparing the rate of grade 3 or higher adverse events in the two study arms. However, no formal stopping rule for safety monitoring is proposed so as to give the DSMB maximum flexibility in balancing the risks and benefits of the treatments.

7.3. Endpoint Analyses

7.3.1. Primary Efficacy Analysis

Objective: To evaluate the relative efficacy of oral CAB/CAB LA (oral run-in and injections, Steps 1 and 2) vs. daily oral TDF/FTC for HIV prevention

Population: mITT population

Outcome: Time of HIV-1 Infection (censored at end of step 2)

Time from randomization to HIV-1 infection (see definition in appendix B) will be the primary endpoint for this analysis. HIV-1 status will be assumed to be negative for any missing visits prior to the first positive HIV-1 test (unless defined differently by the endpoints committee prior to analysis). Person-time and HIV events will be included in this analysis based on each individual's scheduled participation in steps 1 and 2, as determined at randomization. Specifically, individuals who refuse/discontinue injections, pills or both, or who receive open-label study product (e.g. due to pregnancy) will be included in this analysis in their original randomization arm for the duration of their originally scheduled participation in Steps 1 and 2. Individuals who drop out of the study and refuse further testing prior to completion of follow-up and individuals who die prior to completion of follow-up will be treated as uninformatively censored as of their last valid HIV test.

Descriptive analysis: The number of participants, number of infections and cumulative person-years will be presented by arm and overall. The HIV incidence rate will be calculated as the total number of participants with confirmed incident HIV infection during steps 1 and 2 of study follow-up, divided by the person-years accumulated in each arm. Corresponding 95% CIs will be calculated based on Poisson assumptions. Cumulative incidence over follow-up for each arm will be computed using product limit estimates and plotted with 95% CIs.

Statistical Analysis: The primary “intent-to-treat” analysis will be based on a Cox model using time to HIV detection (as defined above) as the outcome. The model will include an indicator for intervention arm (TDF/FTC = 0; CAB LA = 1) and be stratified by site. Consistent with an intent-to-treat analysis, women will be included in the analysis in their original randomization group whenever endpoint information is available within the prespecified timeframe of follow-up. Participants who remain HIV-1 uninfected will be censored at their last negative HIV test. A formal statistical comparison between study arms will be performed using a Wald test of the hypothesis

Ho: HR = 1

Ha: HR < 1

A two-sided test with $\alpha = .05$ will be used. The estimated hazard ratio (HR), a 95% confidence interval, and a p-value for the hypothesis shown above will be given. If the number of events is small (<40) then the p-value will be confirmed using a permutation test based on 100,000 random permutations of the treatment assignments; if there is a meaningful difference between the permutation and asymptotic procedures, the permutation p-value will be used. Treatment efficacy will be estimated as $TE = 1 - HR$.

If the trial is stopped early (prior to the final analysis), then the primary results will be reported as a bias-adjusted mean HR and design-adjusted 95% CI (Emerson S and Fleming TR. Symmetric Group Sequential Test Designs. *Biometrics* 45:904-923, 1989).

7.3.1.1. Sensitivity of the Primary mITT results:

The following sensitivity analyses are proposed to aid in interpretation of the primary ITT results :

- A per-protocol analysis, excluding participants with exclusionary protocol violations, will be conducted if the number of participants affected exceeds 2% of the enrolled population.
Population: Per Protocol
This analysis will be identical to the mITT analysis, except that for partial exclusions, the follow-up will be censored on the last non-missing HIV test result date on or prior to the date of the deviation that resulted in exclusion from the per-protocol population.
- A supportive analysis will be presented using the OBSP censoring in the Injection (Step 2) Efficacy population (see OBSP censoring definitions in appendix B), where study follow-up is censored when a participant does not receive blinded injection study product on time.
- In this active control trial, the superiority of CAB LA is predicated in part on incomplete adherence to daily oral TDF/FTC. Specifically, we assume that overall adherence to TDF/FTC will be less than 50%. If adherence to TDF/FTC is high (greater than 50%) then, as described in section 7.8.4 of the protocol, a supportive non-inferiority (NI) analysis of CAB LA versus TDF/FTC may provide valuable information for interpreting the trial results.

Adherence in the TDF/FTC arm will be measured during the trial in an adherence assessment cohort (see below). If adherence in the TDF/FTC arm is greater than 50% then an NI margin will be computed as described in section 7.8.4.3 of the protocol. The primary analysis described above will then be repeated using the recomputed NI margin instead of 1.0 in the null hypothesis. This supportive NI analysis will not replace the pre-specified primary analysis or change the conclusion of the primary analysis but may provide valuable insight with respect to determining the prevention effectiveness of CAB LA in women.

7.3.1.2. Adherence Assessment Cohort:

A sample of 400 participants in the active TDF/FTC arm will be selected at random during the enrollment period and available plasma samples from selected visits (Step 1: week 4; Step 2: weeks 9, 17, 33, 57, 81, 105, 129, 153, 177) will be assessed for the presence of TDF/FTC and associated metabolites. The TDF/FTC adherence-assessment cohort will be stratified by site or

region and will be selected to ensure uniform representation over the course of the enrollment period. Average, study-wide adherence will be computed as the overall proportion of all tested samples where study drug (TDF/FTC) is detected (i.e. concentrations greater than approximately 0.31 ng/ml).

